4.2 DEFINITION OF BASELINE

Baseline is defined as the last available pre-treatment value taken on or before the day of randomization (Week 2 visit) for all assessments, with the exception of the following efficacy endpoints: patient-reported use of short-acting rescue therapy, and patient-reported daytime asthma symptom severity as measured by Asthma Daily Symptom Diary (ADSD). For these outcome measures, details for derivation of baseline values can be found in [Section 4.5.2](#).

Baseline measurements will be used for the summary of demographic characteristics, as well as for all change-from-baseline analyses of efficacy, safety, and PD endpoints (including change from baseline in FEV1, CGIC, blood eosinophil count, and FeNO, and improvement from baseline in AQLQ(S), ACQ-5, SGRQ, ACQ-7).

For endpoints that are defined in terms of change from baseline or improvement from baseline, patients who do not have a baseline measurement will be excluded from the analyses.

4.3 ANALYSIS OF STUDY CONDUCT

The number of patients randomized will be tabulated by region, country, study site, and treatment arm. Patient disposition (the number of patients receiving the single-blind placebo dose during run-in, randomly allocated, receiving at least one dose of study drug during the double-blind treatment period, completing study treatment during the double-blind treatment period, and completing study visit assessments through Week 54) and time on study will be tabulated by treatment arm. Reasons for premature discontinuation from study treatment and reasons for premature discontinuation from the study prior to Week 54 will be summarized. Eligibility criteria deviations, dosing errors, and other major protocol deviations will be summarized.

4.4 ANALYSIS OF TREATMENT GROUP COMPARABILITY

Demographic and baseline characteristics including but not limited to age, sex, race, ethnicity, blood eosinophil count, number of exacerbations in the prior year, concomitant asthma medication use, pulmonary function, and asthma control (as measured by the ACQ-5), will be summarized for the mITT population by treatment arm using descriptive statistics. Exposure to study drug (number of study drug treatments and duration of treatment) will be summarized for the double-blind treatment period by treatment arm.

4.5 EFFICACY ANALYSIS

Efficacy analyses will be conducted on the mITT population (see Section 4.1.1), with patients grouped according to the treatment assigned at randomization.

Efficacy summaries for the 52-week double-blind treatment period will include data from patients who discontinued study drug early but continued with study assessments and may include data collected at unscheduled visits, early termination visits, or safety follow-up visits, if the visit date occurred within 52-weeks after the randomization visit. For patients completing the Week 54 visits after the schedule Week 54 windows, their Week 54 visits will be considered out-of-window and the corresponding data will be treated as missing.

Comparisons of Interest

Comparisons of efficacy will be performed between each MSTT1041A dose level and the placebo group.

Thus, there will be three comparisons:

[figure not shown]
- MSTT1041A 70 mg with placebo
- MSTT1041A 210 mg with placebo
- MSTT1041A 490 mg with placebo

Hypothesis testing and estimation of treatment effects will be performed with regression models that are fit using data from all four treatment arms and which include three indicator variables to characterize the three treatment comparisons described above.

Type I Error Management

Type I error will be controlled using a fixed sequence testing procedure at the 5% level of significance (two-sided) for primary and secondary efficacy endpoints. For each endpoint the testing procedure will proceed with comparisons from highest to lowest MSTT1041A dose level versus placebo (see [Table 1](#)) in the order specified below.

Table 1 Fixed sequence testing hierarchy

		MSTT1041A		
Endpoint		490 mg	210 mg	70 mg
Primary	Incidence of asthma exacerbation from baseline through Week 54			
Secondary	1. Time to first asthma exacerbation during the 52-week double-blind treatment period			
	2. Absolute change in pre-bronchodilator FEV1 (liters) from baseline to Week 54			
	3. Achievement of improvement in ACQ-5 score at Week 54, defined as a decrease of ≥ 0.5 points from baseline to Week 54			
	4. Absolute change in patient reported daytime asthma symptom severity as measured by the Asthma Daily Symptom Diary (ADSD) from baseline to Week 54			
	5. Proportion of weeks without patient-reported asthma-related nighttime awakenings from baseline through Week 54			
	6. Absolute change in patient-reported use of short-acting rescue therapy from baseline to Week 54			
	7. Achievement of improvement Standardized Asthma Quality-of-Life Questionnaires (AQLQS) score, defined as an increase of ≥ 0.5 points from baseline to Week 54			

The testing procedure will be conducted at a two-sided significance level of 5%. Each hypothesis will be formally tested only if the preceding one is significant at 5% level.

No control of type I error will be applied for the exploratory endpoints, including sensitivity, subgroup, and biomarker analyses. Efficacy analyses will not involve formal comparisons between the three MSTT1041A treatment arms (70, 210, and 490 mg).

Covariate Adjustment

Unless otherwise noted, analyses of efficacy endpoints (primary, secondary, and exploratory) will be adjusted for each of the following covariates:

- Blood eosinophil level at visit 1 ($< 150, \geq 150$ to $< 300, \geq 300$ cells/ μ L)
- Number of asthma exacerbations requiring use of systemic corticosteroids within the 12 months prior to study entry (1–2, ≥ 3 events)
- Total daily ICS dose at visit 1 ($< 1000\mu\text{g}, \geq 1000 \mu\text{g}$ of fluticasone propionate or equivalent)
- Geographic region (North America [United States, Canada], Latin America [Argentina, Mexico, Peru], Central and Eastern Europe [Bulgaria, Czech Republic, Poland, Romania, Russia, Serbia, Ukraine], Western Europe plus Rest of World [Australia, Belgium, France, Germany, New Zealand, South Africa, South Korea]).

No missing data of these baseline covariates are expected. Stratification data collected in the IxRS system, rather than on the electronic Case Report Forms, will be used.

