4.5.12.1 Pre-Bronchodilator Spirometry

Pre-bronchodilator spirometry evaluations should be performed in the morning, before use of bronchodilators. Asthma therapies that may affect spirometry must be withheld until pre-bronchodilator spirometry measurements are completed. Patients must be made aware that bronchodilator use is prohibited within a specified window prior to each clinic visit, with the exception of the screening visit or an unscheduled visit, as follows:

- Twice-daily LABA and twice-daily LAMA: prohibited within 12 hours prior to spirometry
- Once-daily LABA and once-daily LAMA: prohibited within 24 hours prior to spirometry
- SABA or SAMA: prohibited within 4 hours prior to spirometry

With the exception of an unscheduled visit, a patient's visit must be rescheduled if the patient arrives for a study visit having used a bronchodilator within the time window defined above for each medication. To accommodate the rescheduled visit, the usual visit window specified in the schedule of activities (see [Appendix 1](#)) may be extended to ± 4 days for Week 4 or ± 6 days for Week 6–54.

For safety reasons, consideration should be given to omitting spirometry if a patient is having an acute asthma exacerbation event at the time of the scheduled study visit.

Spirometric assessments will include FEV₁, forced vital capacity (FVC), percentage of predicted values for FEV₁ and FVC, FEV₁ to FVC ratio, and average expiratory flow during the middle portion of the expiration (FEF_{25–75}). The percentage of predicted values for FEV₁ and FVC will be derived from the third National and Nutrition Examinations Survey (Hankinson et al. 1999). Each test procedure requires that three valid spirometry maneuvers be performed within 1 hour. The highest FEV₁ and FVC values from the set of three accepted maneuvers will be recorded. Other parameters will be taken from the accepted maneuver with the highest sum of FEV₁ and FVC. A hard-copy report of the spirometry results will be maintained in the patient's medical record.

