Appendix 1 Schedule of Activities

	Screen Visit ^a	Run-In Visit ^b			Double-Blind Treatment Period: Treatment Every 28 (±N) Days ^c														Safety Follow-Up Period		ET Visit ^c	UV ^d
			Pre-Rand.	Post-Rand.															Follow-Up Visit	EoS Visit		
Week	-4 to -2	0	2		4	6	10	14	18	22	26	30	34	38	42	46	50	54	62	70	-	-
(Visit Window in Days) ^e					(±3)	(±5)	(±5)	(±5)	(±5)	(±5)	(±5)	(±5)	(±5)	(±5)	(±5)	(±5)	(±5)	(±5)	(±14)	(±14)	-	-
Visit	1	2	3		4	5	6	7	8	9	10	11	12	13	14	15	16	17	18	19	-	-
Informed consent	x																					
Demographic data	x																					
Medical history and baseline conditions	x																					
Atopy status ^f	x																					
ACQ ^g	x	x	x								x							x				
PGIC ^g											x							x				
AQLQ(S) ^g			x								x							x				
SGRQ ^g			x								x							x				
EQ-5D-5L ^g			x															x				
CGIC ^h											x							x				
Complete physical examination ⁱ	x																					
Limited physical examination ⁱ			x								x							x		x	x	x
Weight (BMI) and height (height at screening only)	x																	x		x	x	
Vital signs ^k	x	x	x		x	x	x	x	x	x	x	x	x	x	x	x	x	x	x	x	x	x

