Appendix 1 Schedule of Activities (cont.)

ACQ = Asthma Control Questionnaire; ACQ-7 = Asthma Control Questionnaire (7 items); ACQ-5 = Asthma Control Questionnaire (5 items); AQLQ = Asthma Quality-of-Life Questionnaire; BMI = body mass index; CGIC = Clinician Global Impression of Change; CT = computed tomography; ECG = electrocardiogram; eCRF = electronic case report form; eDiary = electronic Diary; EoS = End-of-Study; ET = early termination; EQ-5D = EuroQol 5-Dimension Questionnaire; FeNO = fractional exhaled nitric oxide; HbA1c = hemoglobin A1c; HbsAg = hepatitis B surface antigen; HbsAb = hepatitis B surface antibody; HbcAb = hepatitis B core antibody; HCV = hepatitis C virus; IgE = Immunoglobulin E; PCR = polymerase chain reaction; PGIC = Patient Global Impression of Change; PK = pharmacokinetic; PPD = purified protein derivative; PRO = patient-reported outcome; Q4W = every 4 weeks; QFT = QuantiFERON[®] test; Rand. = randomization; RBR = Roche Biosample Repository; SC = subcutaneous; Screen = screening; SGRQ = St. George's Respiratory Questionnaire; TB = tuberculosis; UV = unscheduled visit; WGS = whole genome sequencing.

Notes: On treatment days, all assessments should be performed prior to dosing, unless otherwise specified.

Patients who are unable to tolerate study drug will discontinue study drug but should continue follow-up for all other study procedures and measurements through the end of the study.

^a The screening period may be between 12 and 28 days after study consent, as described in Section 4.5.2.

^b The run-in visit should be scheduled 2 weeks (± 5 days) prior to the randomization visit.

^c Patients who are randomly allocated into the 52-week double-blind treatment period but discontinue study drug should continue follow-up for all other study procedures and measurements through the end of the study. Patients who discontinue from the study prior to Week 50 should return to the site for an early termination visit 4 weeks (± 5 days) after the last dose of study drug and then enter the safety follow-up period.

^d Patients who experience symptoms consistent with an asthma exacerbation as defined in Appendix 12 will be asked to come to the clinic for an unscheduled visit. Patients will be asked to bring a urine sample and will undergo additional evaluations.

^e Visit windows are relative to randomization visit.

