Appendix 1 Schedule of Activities (cont.)

- ^j Perform a limited, symptom-directed examination at specified timepoints or as clinically indicated. Record new or worsened clinically significant abnormalities on the Adverse Event eCRF.
- ^k Includes respiratory rate, pulse rate, and systolic and diastolic blood pressure while the patient is *ideally* in a seated position, and temperature. Record abnormalities observed prior to dosing at Visit 2 on the General Medical History and Baseline Conditions eCRF. At subsequent visits, record new or worsened clinically significant abnormalities on the Adverse Event eCRF.
- ^l If mean QTcF is >500 ms and/or >60 ms longer than the baseline value, a PK sample will be obtained (if the visit does not already include a scheduled PK sample), see Section 4.5.9. All ECGs are to be obtained prior to other procedures scheduled at that same time (e.g., blood draws). Circumstances that may induce changes in heart rate, including environmental distractions (e.g., television, radio, conversation) should be avoided during the pre-ECG resting period and during ECG recording.
- ^m Patients will use an electronic diary ("eDiary") to record assessments twice a day: in the morning, diary items are asthma symptoms experienced during the night (Asthma Daily Symptom Diary - nighttime), nighttime awakenings, and short-acting rescue medication use, and a single item assessment of overnight symptom severity (PGIS). In the evening, daytime symptom severity (Asthma Daily Symptom Diary - ADSD daytime symptoms), short-acting rescue medication use, and a single-item assessment of daytime symptom severity. Most daily diary items will be completed everyday through Week 54. A single-item compliance with daily controller medication will also be included in the evening diary.
- ⁿ On the days of study visits, if the patient had not performed the morning PEFr measurement before arrival at the clinic, the PEFr should be measured at the clinic.
- ^o A patient's visit must be rescheduled if the patient has used a bronchodilator within the time window defined in Section 4.5.12.1. To accommodate the rescheduled visit, the usual visit window during the treatment period may be extended to ± 4 days for Week 4 or ± 6 days for Weeks 6–54.

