The proportion of patients who achieve a clinically meaningful improvement in AQLQ(S) (improvement of ≥ 0.5 points from baseline) at Week 54 will be summarized by treatment group and timepoint. AQLQ(S) at randomization visit (Week 2) will be used as the baseline AQLQ(S) score. A logistic regression model, with terms for treatment group, baseline AQLQ(S), and the baseline covariates described in Section 4.5 will be used to compare MSTT1041A with placebo. For patients without a Week 54 assessment of AQLQ(S), the Week 26 score will be used. Patients without a post-randomization assessment (Week 26 or Week 54) will be excluded from the analysis. Point estimates, 95% CIs, and p-values for the treatment difference (MSTT1041A vs. placebo) will be calculated for each MSTT1041A dose level.

Considering each dose level separately, if a statistically significant difference between MSTT1041A and placebo is observed at Week 54, then a test for significance will be performed at Week 26. This procedure will be used to determine the earliest timepoint at which significance is observed (comparing MSTT1041A with placebo), and considered the time of onset of sustained AQLQ(S) improvement.

Asthma Control Questionnaire

Asthma control, as measured by the ACQ, will be assessed by asking patients to recall their experience with asthma during the previous week. The full ACQ consists of seven questions: five questions related to symptoms (i.e., nighttime awakening, asthma symptoms upon awakening in the morning, activity limitation, shortness of breath, and wheezing frequency), one question about use of short-acting rescue therapy, and one question about FEV₁ (to be completed by site staff). The items are scored on a scale ranging from 0 (totally controlled) to 6 (extremely poorly controlled). The items are equally weighted. For the ACQ, higher scores indicate worse control, and 0.5 points is considered the MID. The ACQ can be scored two ways: 1) the mean of the five symptom-related items (ACQ-5); or 2) the mean of all 7 items (ACQ-7).

The proportion of patients who achieve a clinically meaningful improvement in asthma control based on the ACQ-5 (decrease of ≥ 0.5 points from baseline) will be analyzed using the same methodology as described for achievement of improvement from baseline at Week 54 in AQLQ(S). ACQ-5 at randomization visit (Week 2) will be used as the baseline ACQ-5 score.

Asthma Rescue Medication Use

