early. An event count corresponding to each unobserved period will be imputed by first fitting a negative binomial generalized linear model to the observed data and sampling from the posterior distribution of the model parameter estimates. These sampled parameter estimates along with the patient-specific observed covariate values, observed exacerbation counts, and length of unobserved interval will be used in conjunction with a random number generator to impute an event count for the unobserved time period, which is added to the observed event count (Keene et al. 2014). These augmented datasets will be analyzed according to the model described in Section 4.5.1 and the results combined using Rubin's rules.

- In the tipping point sensitivity analysis, the underlying event rate used to impute unobserved event counts for a given arm will be adjusted via a multiplier delta; a separate delta will be applied to each arm. A range of delta values will be used to adjust the underlying event rate used for imputation in the MSTT1041A and placebo arms independently based on a grid of delta adjustments. The delta values will be chosen on the basis of the treatment effect (rate ratio) observed for a given MSTT1041A arm compared with placebo from the analyses described in Section 4.5.1. The range of delta values will include cases where dropouts from the MSTT1041A arm are assumed to have worse outcomes than dropouts from the placebo arm. For each endpoint, the resulting point estimates of treatment effect and corresponding p-values under each pair of deltas for each MSTT1041A and placebo comparison will be tabulated.

Also, for the secondary endpoint (absolute change from baseline in FEV₁), a cumulative responder plot which displays, by treatment arm, the proportion of patients who achieve each specified absolute change in pre-bronchodilator FEV₁ from baseline at Week 54 for a range of possible FEV₁ changes will be provided. For this plot, patients with missing Week 54 data will be assumed to be non-responders.

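### Week 54 data collected after the visit window are set to missing, so measured late AQLQ(S) and ACQ-5 scores give way to Week 26 scores 196 days older, and no planned analysis restores them

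*SAP*

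**What the plan says.** SAP 4.5 (Efficacy Analysis) states that when Week 54 is completed after its scheduled window, "their Week 54 visits will be considered out-of-window and the corresponding data will be treated as missing". The rule is one-sided: it covers late visits only. The supplied SAP text gives no number of days. The sentence before it sets a different limit, 52 weeks after randomization, for data from unscheduled, early termination and follow-up visits.

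The window itself is in the protocol. The "Visit Window in Days" row of Appendix 1 gives ±5 for Week 54, and footnote e adds: "Visit windows are relative to randomization visit". Under Protocol 4.5.12.1 a patient's "visit must be rescheduled if the patient arrives for a study visit having used a bronchodilator within the time window" for that drug. Footnote o of Appendix 1 says that in this case "the usual visit window during the treatment period may be extended to ± 4 days for Week 4 or ± 6 days" for Weeks 6–54.

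Once the Week 54 value is missing, the SAP acts as follows:

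- **AQLQ(S) (4.5.2):** "For patients without a Week 54 assessment of AQLQ(S), the Week 26 score will be used", and "Patients without a post-randomization assessment (Week 26 or Week 54) will be excluded from the analysis".
- **ACQ-5 (4.5.2), SGRQ and ACQ-7 (4.5.3):** same method as AQLQ(S). CGIC has its own equivalent Week 26 substitution.
- **FEV1 (4.5.2, 4.8):** no imputation; missing values are left to the MMRM.
- **FEV1 cumulative responder plot (4.5.4):** "For this plot, patients with missing Week 54 data will be assumed to be non-responders".

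The primary endpoint is handled differently. Its time at risk runs to the actual Week 54 visit (4.5.1), and time to first exacerbation is censored at the end of that period (4.5.2).

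**The concern.** A patient who attends a few days late has been measured. The plan discards that measurement and uses something less informative: a score from half a year earlier, a model prediction, or an assumed failure. AQLQ(S) and ACQ are collected after randomization only at Weeks 26 and 54, so no nearer substitute exists.

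Lateness may also be related to outcome. A visit must be rescheduled when the patient has recently used a bronchodilator, including rescue medication within 4 hours, and only one extra day is allowed for it. Rescue use reflects symptoms, so missingness created by this rule need not be random. The documents do not show that it differs by arm.

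At stake are precision and responder classification for secondary and exploratory endpoints. In the fixed sequence (SAP Table 1), FEV1 and ACQ-5 come after the primary endpoint and time to first exacerbation, and AQLQ(S) is last.

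**Working it through.** The plan gives no figure for late visits, nor any power for FEV1 or ACQ-5, so there is no stated number to reproduce. Steps 1 and 2 use the documents alone. Steps 3 to 6 rest on the assumptions named in each.

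**1. Calendar.** Randomization is at Week 2, so Week 26 is day (26−2)×7 = 168 and Week 54 is day (54−2)×7 = 364. The nominal gap is 364−168 = 196 days. The first late day is 370 (±5) or 371 (±6). From that day, a Week 26 score taken within its own window is 370−173 = 197 to 370−163 = 207 days older (±5), or 197 to 209 days older (±6). A value measured on day 370 is 6 days from the Week 54 target.

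**2. Does any planned analysis use the late value?** SAP 4.5.4 contains three kinds of analysis:
- a negative binomial model, for the primary endpoint only;
- tipping-point analyses, which impute missing data, run only for endpoints found significant, and for continuous endpoints shift post-dropout imputed values;
- the FEV1 plot, which counts missing as non-response.

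None restores a measured late value. SAP 4.3 plans no table of late visits.

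**3. Numbers affected.** 502/4 = 125.5 per arm (SAP 2.2). If the planned 15% dropout means no Week 54 visit, 125.5×0.85 = 106.7 attend. With an assumed 5–10% late, 5.3–10.7 per arm lose the value.

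**4. Responder status.** Assume bivariate normal change scores with SD 1, mean change −0.6 to −1.0, Week 26-to-54 correlation 0.5–0.7, and response at a decrease of at least 0.5. Status differs between the two visits in 22.2–33.2% of patients: 5.3×0.222 = 1.2 up to 10.7×0.332 = 3.5 patients per arm, in either direction.

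**5. Responder difference.** For each arm, the analyzed rate is (1−s)×p54 + s×p26, where s is the late share. Assume true Week 54 rates of 65% vs 50%.

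| Late share (active / placebo) | Week 26 rates | Analyzed difference, points |
|---|---|---|
| equal | same as Week 54 | 15.0 |
| 5% / 5% | 55% vs 50% | 64.5 − 50.0 = 14.5 |
| 10% / 10% | 55% vs 50% | 64.0 − 50.0 = 14.0 |
| 5% / 10% | 55% vs 40% | 64.5 − 49.0 = 15.5 |
| 10% / 5% | 55% vs 40% | 64.0 − 49.5 = 14.5 |

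A two-proportion z test with 106.7 per arm at two-sided 5% has power 0.602, 0.572 and 0.542 at 15.0, 14.5 and 14.0 points. An unpooled variance gives 61%, 58% and 55%; the loss is the same.

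**6. FEV1.** Approximate information loss is s×(1−ρ²), with ρ the assumed adjacent-visit correlation: 0.05×(1−0.81) = 0.95% to 0.10×(1−0.49) = 5.1%. An assumed 80% power becomes 79.6% to 77.9%. In the cumulative plot, at a cut-off reached by 65% vs 50%, the 15-point gap is drawn as (1−s)×15 = 14.25 (5% late) or 13.5 (10% late).

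**The case against.** The strongest reply is that a strict pre-specified window keeps Week 54 values close to treatment and that relaxing it has its own cost. The last scheduled dose is at Week 50 (day 336). A visit 14 days late falls 42 days after it, against 33–34 days at the window limit. AQLQ(S) recalls 2 weeks, so at +14 days it covers days 28–42 after that dose, wholly beyond the 4-week dosing interval. If a 15-point responder difference faded by 10–50% over those days, 5–10% late visits would cost 0.05×0.10×15 = 0.075 to 0.10×0.50×15 = 0.75 points, the same order as the harm alleged. The 14-day figure is borrowed from the follow-up visits.

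The late share is also unknown. At 1–2%, only 1–2 patients per arm are late, 0.2–0.7 per arm change status, and the adverse shift is −0.1 to −0.2 points. The FEV1 loss is probably overstated, because the MMRM uses all of a patient's visits and reports every visit. The plot is descriptive.

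Most of this stands as a limit on size, and the recall point is a good reason to keep the bound modest and to repeat the analysis with the strict window. It does not justify the substitute: for AQLQ(S) and ACQ-5 the choice is between a score days from the target and one 196 days from it. The tipping-point analyses do not answer the point either, since they vary assumptions about values that were in fact observed.

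**Conclusion.** The concern holds. The text discards measured Week 54 values from late visits, puts much older scores in their place for five questionnaire or global-rating endpoints, and plans no analysis that recovers them. The SAP also treats one and the same late visit as valid for time at risk and as missing for other endpoints, and does not say whether the cut-off is 5 or 6 days.

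The consequence is modest: some loss of precision and added misclassification. Under the assumptions above, the responder difference moves by 0 to −1.0 points with equal lateness and by ±0.5 points with unequal lateness, and FEV1 power falls by at most about 2 points. Size and direction cannot be settled from the documents, which give no late share, SD or correlation. The primary endpoint and time to first exacerbation appear unaffected. The change should be made because it is cheap, but the trial's main conclusion does not depend on it.

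**What to change.** Replace the sentence in SAP 4.5 as follows:

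- **Main analysis:** use an observed late Week 54 value up to a stated modest bound, for example 14 days after the target, the tolerance Appendix 1 gives Weeks 62 and 70. Fall back on Week 26 only if no Week 54 value lies within the bound. Apply the same rule to the FEV1 MMRM and the cumulative plot.
- **Sensitivity analyses:** repeat with the strict protocol window, naming 5 or 6 days, and with a wider bound under 28 days. Week 62 is day 420, so the midpoint between Weeks 54 and 62 is (420−364)/2 = 28 days after target.
- **Reporting:** tabulate late Week 54 visits by arm and reason.
- **Clarification:** confirm that the rule does not reach the primary endpoint or time to first exacerbation.

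The cost is SAP wording and minor programming, with no new data. The price is the possible dilution of about 0.1 to 0.75 points set out above, which the strict-window repeat would reveal. SAP Section 1 bars changes at or after the 54-week analysis, so the edit must precede it.
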